#### **Working Memory Span (EF-Touch: Houses game)**

This task measures working memory and is based on work from Kane & Engle, 2003. Working memory involves holding information in short-term storage and attending to one item while overcoming interference from the other. In this task, children are presented with pictures of houses with animals and colors in them. The child is asked to name the type of animal and color in each of the houses and then, after a short delay, the house is presented again - but this time the house is empty. The child is asked to recall only one piece of information (e.g., either the color or the animal that was in the house). The task requires children to perform the operation of naming and holding in mind two pieces of information simultaneously and to activate one while overcoming interference occurring from the other. The task becomes more difficult as the number of houses increases. In the pretest phase, it is established that children can name both the colors and the animals in the task. Children then receive three 1-house trial, three 2-house trials, and three 3-house trials. There are 18 items. The score on this activity is a proportion from 0 to 1, zero indicating no items correct and 1 indicating all items were correct.

#### **Attention-Shifting Performance (EF-Touch: Something's the Same game)**

This task measures attention shifting and requires children to use flexible thinking. It was adapted from the Flexible Item Selection Task developed by Jacques and Zelazo (2001). For the initial trials in the task, children are presented with two pictures (animals, flowers, etc.) that are similar along a single dimension of color, shape, or size. Initially, the child is explicitly told how two of the pictures are the same in some way. Then, the child is then presented with a third picture alongside the original two and asked to state how the new picture is similar to one of the original pictures (e.g., if the first two pictures were similar along the dimension of shape, the third card would be similar to one of the first two along the dimension of color or size). This task requires the child to shift his/her attention from the initial dimension of similarity to a new dimension of similarity. In the most difficult items all of the pictures are presented at once and children are prompted to identify both dimensions of similarity. There are 30 items. The score on this activity is a proportion from 0 to 1, zero indicating no items correct and 1 indicating all items **were correct**.

#### **Inhibitory Motor Control (EF-Touch: Pigs game)**

This task measures inhibitory motor control and is a standard go no-go task (Durstun, Thomas, Yang, Ulug, Zimmerman, & Casey, 2002). Children are presented with a large green button on the screen that makes a "popping" sound when it is touched. Children are instructed to touch the button every time that they see an animal (the 'go' response) except when that animal is a pig (the 'no-go' response). No-go responses vary in difficulty depending on how many go responses preceded them. In the pretest phase, children are asked to identify all of the animals. During administration items, the task is presented in varying numbers of go trials prior to each no-go trial, including, in standard order, 1-go, 3-go, 3-go, 5-go, 1-go, 5-go, 7-go and 7-go. There are 40 items. The score on this activity is a proportion from 0 to 1, zero indicating no items correct and 1 indicating all items were correct.

Statistical procedures will include comparisons of outcomes between the treatment and control groups. Given the small nature of the sample, and concomitantly limited statistical power that entails, our analyses will focus on understanding patterns of associations across outcomes rather than a strict focus on statistical significance. That said, formal tests of significant differences will still be performed.

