## Statistical Procedures:

**Measures:** We plan to conduct a baseline assessment late in the third trimester of pregnancy (weeks 28-34) as an in-person home visit and a follow up survey over the phone when the baby is ten months, twenty-five, and forty-two months old. Our measures fall within five main categories: 1) Demographics; 2) Financial security; 3) Maternal mental health and stress; 4) Parenting quality, and 5) Child Outcomes.

**1) Demographics:** We will measure a standard set of demographic variables at baseline, including age, a full household roster (age, gender, and relationship to respondent for all members of the household), education, employment, race/ethnicity, immigration status, and a global measure of total household income.

**2) Financial security:** We will collect detailed measures of financial stress and material hardship. Financial stress measures will be adapted from the Fragile Families and Child Wellbeing Study, while material hardship measures will be adapted from the Survey of Income and Program Participation, the Fragile Families study, and the Robin Hood Poverty Tracker. Hardship measures will include indicators of food insecurity, housing hardship, utility hardship, medical hardship, and general financial hardship (e.g., running out of money between pay cycles). We also plan to develop new measures of frequency and intensity of hardships in order to capture gradations beyond simple yes/no measures that are standard in the literature.

**3) Maternal mental health and stress:** We will measure maternal depression and stress both at baseline and follow-up with identical measures.

The Parenting Stress Index Short Form (PSI) was developed based on the theory that total parental stress is a function of child and parent characteristics, as well as situational variables. The short form contains 36 items in three main domains: parental distress, parent-child dysfunctional interaction, and difficult child. The total parenting stress score describes the overall level of parenting stress that an individual is experiencing. Internal consistency (Cronbach's alpha) for the PSI (Short-Form) ranges from 0.80-0.91 and test-retest reliabilities from 0.68-0.85. In the 10 month survey we will only include the attachment subscale.

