Additional funding has allowed for the expansion of recruitment size; we have recruited and enrolled 160 treatment group subjects and 160 control group subjects. Treatment and control group subjects will both be given an incentive of \$50.00 in cash for their participation in the 45 minute survey, and control group subjects will also be given a gift tote filled with approximately \$75.00-\$100 worth of developmentally-appropriate gifts for their impending child (this being the only difference between the treatment and control group consent forms attached to the protocol – the different versions of the consent forms only differ in their description of the compensation offered). Study participants who are selected in the RtG lottery will receive a follow-up call from RtG informing them of their selection, and Columbia staff will call the participants who do not receive a place in the lottery and invite them to remain part of the study approximately four business days after completing the baseline survey.

Experienced interviewers will conduct the interviews in either English or Spanish. Subjects will be enrolled in the “Columbia Mothers and Babies Study” and follow-up permission and information will be collected at that point (i.e., subjects will be asked for best modes of future contact and have the opportunity to provide friends’ and family members’ contacts, email addresses, etc.). Approximately 4 months after the completed baseline interview, subject will be mailed a jotter and a letter with Columbia’s contact information so that participants can reach out with updated contact information. Approximately 9-10 months after the baby is born, participants who agreed will be followed up with on the phone and will be asked to participate in a 40 minute survey with a \$35 incentive. Due to the transient nature of this study sample, we anticipate that it will be more difficult to reach some subjects than others. For subjects that do not refuse, but who have not completed the follow-up survey after 10 attempts, we will be offer an additional \$15 incentive, bringing the total compensation to \$50.

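### The stated analysis gives baseline values no role, although depression and stress are measured identically at baseline and follow-up and the plan says power is limited

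*Combined protocol and SAP*

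**What the plan says.** The quantitative analysis is described in one place, the closing paragraph of Statistical Procedures, printed after the description of the Pigs game. It says "Statistical procedures will include comparisons of outcomes between the treatment and control groups". It then gives a reason for not concentrating on significance: "Given the small nature of the sample, and concomitantly limited statistical power that entails". It adds that "formal tests of significant differences will still be performed". It names no model, estimator, covariate or method for the repeated waves. The Data paragraph under Study Design says that survey, administrative and visit data will form one dataset, but not how that dataset will be analysed. The later Data analysis heading covers qualitative coding only.

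On baseline data, Statistical Procedures says "We will measure maternal depression and stress both at baseline and follow-up with identical measures" and "We will measure a standard set of demographic variables at baseline". The demographic list includes age, household roster, education, employment, race/ethnicity, immigration status and household income. One stress instrument is an exception to the identical-measures statement. For the Parenting Stress Index (PSI) the plan says "In the 10 month survey we will only include the attachment subscale".

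On size, section 2, Study Design and Statistical Procedures, says "we have recruited and enrolled 160 treatment group subjects and 160 control group subjects".

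**The concern.** Where an outcome has been measured before treatment with the same instrument, comparing arms on the follow-up score alone is valid under randomisation. It is less precise than a comparison adjusted for the baseline score, and it leaves any chance baseline difference in the estimate. This study says that power is its main limitation and already takes the baseline measurement, yet the plan gives that measurement no part in the treatment comparison.

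There is a second cost. If adjustment is left open, the choice between adjusted and unadjusted results can be made after the data are seen, across many outcomes and three survey waves.

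**Working it through.** **Is there a figure to reproduce?** No. The documents give no power, effect size, standard deviation, significance level or derivation of the sample size. The 160 per arm is a recruitment number.

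**Inputs**
- n = 160 per arm, 1:1 (section 2, Study Design and Statistical Procedures).
- Two-sided significance level 0.05 and 80% power: assumed.
- Effect for the power calculation 0.25 SD: assumed, for illustration.
- r, the correlation between a mother's score in late pregnancy and her score 10 to 42 months after birth: not in the documents, assumed 0.2 to 0.7. The test-retest value of 0.95 quoted for the PSS is a reliability and is not used.
- Loss to follow-up: no rate is given, though the plan says "Due to the transient nature of this study sample, we anticipate that it will be more difficult to reach some subjects than others". Zero and 30% are shown (30% assumed; 160 × 0.7 = 112 per arm).

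**Formulas.** ANCOVA on the baseline value multiplies the variance of the treatment comparison by 1 − r². Then:
- detectable effect in SD units = (1.960 + 0.842) × √(2/n) × √(1 − r²)
- power at 0.25 SD = Φ(0.25 / [√(2/n) × √(1 − r²)] − 1.960)
- equivalent unadjusted n per arm = n / (1 − r²)

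**Unadjusted, 160 per arm.** √(2/160) = 0.1118. Detectable effect = 2.802 × 0.1118 = 0.313 SD. Power at 0.25 SD = Φ(2.236 − 1.960) = 60.9%.

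**Adjusted, r = 0.5.** √0.75 = 0.866, so the standard error falls 13.4%. Detectable effect = 0.313 × 0.866 = 0.271 SD. Power = Φ(2.582 − 1.960) = 73.3%. Equivalent n = 160/0.75 = 213 per arm.

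| r (assumed) | Variance factor | Detectable effect, 160 per arm | Power at 0.25 SD, 160 per arm | Equivalent n per arm | Detectable effect, 112 per arm |
|---|---|---|---|---|---|
| unadjusted | 1 | 0.313 | 60.9% | 160 | 0.374 |
| 0.2 | 0.96 | 0.307 | 62.6% | 167 | 0.367 |
| 0.3 | 0.91 | 0.299 | 65.0% | 176 | 0.357 |
| 0.5 | 0.75 | 0.271 | 73.3% | 213 | 0.324 |
| 0.6 | 0.64 | 0.251 | 79.8% | 250 | 0.300 |
| 0.7 | 0.51 | 0.224 | 87.9% | 314 | 0.267 |

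**Which outcomes does the table cover?**
- CES-D and PSS: yes, on the plan's own statement that depression and stress are measured identically.
- PSI: not on this basis. Only the attachment subscale is used at 10 months, and attachment to the focal child cannot be measured before birth.
- Hardship and financial stress: only for items that were asked at baseline, which the Financial security paragraph does not state.
- Parenting of the focal child, vocabulary, executive function and the three-bag task: no. These have no pre-birth value, so only other baseline variables can help.

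**The case against.** **Silence is not a decision.** A reader might infer that the plan prescribes an unadjusted comparison and so throws precision away. The text does not say that. It never uses a word such as raw or unadjusted, its list of procedures is not exclusive, and one combined dataset is compatible with an adjusted model. This part of the objection stands. The point is that baseline values are given no role, not that they are ruled out.

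**The study does not decline to test.** A reader might also infer that low power is used as an excuse to avoid significance tests. The closing paragraph says formal tests will be done.

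**The gain is not on the main questions.** The three research questions concern hardship and financial stress, the home environment and interactions with the child, and connection to services. Depression and general stress are in none of them. This stands: the table must not be read as the power lost by the study as a whole.

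**The size is assumed.** At r = 0.2 the standard error falls only 2%, and with pregnancy and at least 10 months between the measurements a low r is possible. This also stands, and is why a range is shown.

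**The baseline survey follows randomisation.** Under Informed Consent Process, mothers are randomised when they schedule the visit. The consent form read before the survey differs by arm, because controls are offered a tote bag, so an interviewer could infer the arm. Participants learn their lottery result only about four business days after the survey, so the scores are reasonable covariates, but the plan should acknowledge the sequence.

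**The data are not all in hand.** The documents report completed enrolment, while the follow-up procedures are written in the future tense. The change is still one of wording.

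**Conclusion.** The concern holds in a limited form. The plan assigns baseline values no part in the treatment comparison, although it measures depression and stress identically before and after and says its power is limited. For CES-D and PSS, ANCOVA on the baseline score is a more precise method than the one stated and needs no added measurement.

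The gain is small at r = 0.3 (power at 0.25 SD up about 4 points), and material at r = 0.5 (up about 12 points) or r = 0.6 (up about 19 points). With an assumed 30% loss the detectable effects are larger, but the proportional gain is the same: 0.374 to 0.324 SD at r = 0.5. All of this rests on an assumed r, an assumed two-sided 0.05, and a roughly linear relation between baseline and follow-up scores.

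No gain has been computed for parenting and child outcomes; it is probably smaller. An unadjusted analysis would remain valid, so this is an improvement the plan should adopt and not a flaw that undermines the trial.

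**What to change.** Add to the closing paragraph of Statistical Procedures:

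1. For CES-D and PSS at 10, 25 and 42 months, estimate the treatment effect by ANCOVA with the mother's baseline score on the same measure as covariate. Do the same for any hardship or financial-stress item that was asked at baseline, and list those items.
2. For parenting and child outcomes, adjust for a short set fixed in advance from baseline variables the plan already lists, for example household income, education, and baseline CES-D and PSS. State that a smaller gain is expected.
3. State that randomisation precedes the baseline survey, that the consent forms differ by arm in compensation, and that participants learn their lottery result about four business days after the survey.
4. Keep randomised mothers with missing baseline values in the analysis by a simple rule, such as a missing indicator or imputation. Skipped items are to be expected because any question may be skipped. Say also that scores from a replacement caregiver at 25 or 42 months are not paired with the mother's baseline.
5. Report the unadjusted comparison alongside as a secondary result.

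A joint mixed model over the waves is optional; separate ANCOVAs per wave are enough. The cost is plan wording only, and the change should be dated before outcomes are compared by arm. It needs no new data and no change to study conduct.

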## **Procedures**

Study Description

## 1. Study Purpose and Rationale

This study is funded by the Robert Wood Johnson Foundation, an organization that is committed to the betterment of health and wellbeing among all populations in the US. The purpose of the research is to provide an evidence-based evaluation of the unique Room to Grow model and measure its impacts on the health and wellbeing of disadvantaged mothers and babies.

The Room to Grow model combines both parenting supports and meaningful provision of material support-- the study will objectively assess whether a combined approach can prove potentially more powerful than the sum of its parts.

Our project is designed to investigate proximal outcomes. Over the long-term, our team hopes to build upon these proximal outcomes and to eventually follow children through school-age, as well as greatly expand the number of children that are included in the RCT project.

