## Background

### Study Purpose and Rationale:

**Study Purpose:** Our research project is to launch a small-scale randomized controlled trial (RCT) of an innovative program in New York City called Room to Grow (RtG). RtG's mission is to enrich the lives of babies born into poverty throughout their critical first three years of development. The research-informed program model combines tailored, one-on-one sessions with an expert clinical social worker in-person every three months plus ongoing communication (phone and email), provision of essential baby items including books, toys, clothing, and equipment (retail value of in-kind items over three years averages \$10,000), and connections to vital community resources (e.g., housing, entitlements, child care, social services). The goal of RtG's innovative program is to help parents increase the probability that their children will enter school ready to learn and continue on to meet their full potential in education, work, and citizenship. The therapeutic, psychodynamic approach and robust three-year long relationship with families is designed to act as the catalyst for sustainable, long-term change in parenting methods and family system stability. Critically, and in contrast to other programs aimed at improving parenting and child development, RtG believes that providing concrete material assistance enhances the effectiveness of counseling and referrals to low-income families by reducing economic stress and freeing up scarce resources. The program builds on decades of research on the importance of parenting supports for low-income families and their children, the significance of concrete material support and poverty reduction in enhancing children's health and development, and the recognition that the early years are an effective time to provide critical supports that influence long-term outcomes. Numerous programs, such as home-visiting models that provide parenting supports to low-income new mothers have shown promising results (Cates et al., 2016; Peacock et al., 2013). After decades of correlational research establishing relationships between income, poverty, and children's health and development, there is an emerging literature providing convincing causal evidence that income matters for child outcomes (Duncan, Morris, and Rodgrigues, 2011; Chaudry and [name], 2016). Both strains of this research build upon additional research that clearly suggests early childhood is a key period of vulnerability where interventions can make a lasting difference in the fortunes of low-income children and their families (Duncan, Magnuson, Kalil, and Ziol-Guest, 2012). Our research will build upon this literature, by testing an intervention that combines *both* parenting supports and meaningful provision of material support - in essence, assessing whether a combined approach can prove potentially more powerful than the sum of its parts. **Research Questions:** Given the topic outlined above, our research will provide answers to a number of important research questions. 1) Does random assignment to RtG alleviate parents' experiences of material hardship and financial stress? 2) Does random assignment to RtG enhance the quality of parents' home environment and interactions with children? 3) Does random assignment to RtG enhance parents' connection to essential community and health services? It should be noted that our project is designed to investigate proximal outcomes. Over the long-term, our team hopes to build upon these proximal outcomes and to eventually follow children through school-age, as well as greatly expand the number of children that are included in the RCT project.

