
**Rationale: Knowledge Production:** The evaluation of RtG provides the unprecedented opportunity to test the combined value of parenting education with social and material supports. Our project leverages an innovative approach that combines income supports, parenting education and connection to community services to promote the early health and development of young children. Both parenting and income support programs each aim to promote low- and moderate income families' positive health and development, but too often they work in isolation, potentially limiting their ability to reduce disparities in both parents' and children's health and development. RtG's innovative model provides an opportunity to test the combined effect of these services, and provide valuable information to practitioners and policy makers on the synergistic effects of these program components. It also provides a low-cost model compared to existing home-based interventions. The proposed research can facilitate change in the early childhood field by demonstrating preliminary evidence that this innovative model can achieve demonstrable effects on key proximal outcomes over the first year of life and provide a first step towards building the evidence for multipronged approaches to meeting the needs of low-income families. Findings from this study may guide the field towards more integrated approaches that combines material support, connection to resources, and parenting assistance to make real impacts in the health and development of young children.

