## 2. Study Design and Statistical Procedures

Our study will consist of a small-scale RCT of RtG in New York City (RtG also has a Boston site that will not be currently part of the study). Late-term pregnant mothers are typically referred to RtG from outside service providers, most of which are hospital staff across New York City and a few non-profits. From these referral forms, select directory information is entered into a Google document that is shared with Drs. [name], [name], and their staff: client's first and last name, due date, referral date, phone number and email, age bracket of over or under 18, and referral agency. No other information, including any health-related information, is passed on to Columbia staff. Columbia staff then initiate contact with referred clients—after a client agrees to study participation and schedules their baseline survey appointment they are randomized by Columbia staff to either the treatment or control group. If a client refuses study participation the client is not randomized by Columbia staff and the referral is passed back to Room to Grow, where the referral is randomly assigned to either be in our out of the program; this process ensures that all referrals undergo randomization regardless of their decision to participate in the study. The treatment group will consist of mothers that were randomly selected to receive Room to Grow services, which include three years of social and practical support for the mother and baby. Mothers in the control group will not receive Room to Grow services. Room to Grow receives more referrals than they can accommodate at any given time, so the randomization process is a fair and equitable system for assigning mothers program slots. As stated above, a participant's decision to partake in the Columbia Study will not affect their chance of receiving Room to Grow services—mothers who refuse to participate in the study are passed back to Room to Grow, where they are randomly assigned in or out of the program. Room to Grow uses a pre-generated list of slot assignments of either “in” or “out”—when a referral is passed back its consecutive position on the list indicates if the referral is accepted into the program.

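### The two-arm design estimates the effect of the full Room to Grow package and cannot support the sum-of-parts and synergy statements in the purpose, rationale and abstract

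*Combined protocol and SAP*

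**What the plan says.** The combined protocol and SAP states a sum-of-parts aim in three places and a synergy aim in a fourth:

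- Procedures, section 1 (Study Purpose and Rationale): "the study will objectively assess whether a combined approach can prove potentially more powerful than the sum of its parts".
- Background, Study Purpose: "in essence, assessing whether a combined approach can prove potentially more powerful than the sum of its parts". The Scientific Abstract carries the same clause.
- Background, Rationale: Knowledge Production: the model will "provide valuable information to practitioners and policy makers on the synergistic effects of these program components".

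The design is in Procedures, section 2. Mothers who agree to take part and schedule the baseline survey are handled as follows: "they are randomized by Columbia staff to either the treatment or control group". On the content of the arms: "The treatment group will consist of mothers that were randomly selected to receive Room to Grow services", and "Mothers in the control group will not receive Room to Grow services". Controls do receive a gift tote worth about $75 to $100 and a mental-health resource flyer. Statistical Procedures plans comparisons of outcomes between the two groups and nothing by component.

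Other statements are narrower. The opening paragraph of section 1 gives the purpose as evaluating the RtG model and measuring its impacts. The three research questions, in the Background and under Research Question(s)/Hypothesis(es), each ask what random assignment to RtG does.

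**The concern.** To say that a combination exceeds the sum of its parts, one must know what each part does alone. No arm in this trial receives parenting support alone, goods alone or referrals alone, and no external estimate of a component effect is brought in. The documents therefore claim an assessment that the design cannot make.

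What is at stake is interpretation. The Background expects the findings to steer the field towards integrated approaches and to inform income-support and parenting programs about combining features of both. Some planned outcomes could move through a single component. StimQ has a subscale on the availability of learning materials, and RtG supplies books and toys. Material hardship could respond to goods averaging $10,000 in retail value over three years, with no contribution from counselling. Under the present wording, a benefit on such measures could be read as evidence of synergy when it shows only that the package did something.

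**Working it through.** The documents give no figure to reproduce, because this is a question of what can be estimated.

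**Inputs from the documents.** There are two arms of 160 (section 2). The treatment arm receives three components together (Background): clinician sessions (P), in-kind goods (M) and community referrals (R). The control arm receives no RtG services.

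**Model.** Let P, M and R each be 0 or 1. A full model has 2 × 2 × 2 = 8 cell means and so 8 parameters. The trial observes two cells, (0,0,0) and (1,1,1). The expected arm difference is

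D = (bP + bM + bR) + S, where S = bPM + bPR + bMR + bPMR.

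The bracket is the sum of the parts and S is the synergy. The sum-of-parts aim is a statement about the sign of S. The data give D only, which is one equation for seven unknown effects.

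Merging the components into two parts (parenting support and goods) does not rescue the aim. The design rows are then (1,0,0,0) and (1,1,1,1), with rank 2 for 4 parameters. Adding the interaction contrast (0,0,0,1) raises the rank, so the interaction is not estimable. With all four cells of a 2×2 factorial the rank is 4 and it is estimable.

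**Illustration.** Assume a package effect of 0.30 SD (not from the documents) and, for simplicity, bR = 0:

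| bP | bM | Sum of parts | S | D |
|---|---|---|---|---|
| 0.30 | 0 | 0.30 | 0 | 0.30 |
| 0.15 | 0.15 | 0.30 | 0 | 0.30 |
| 0.05 | 0.05 | 0.10 | +0.20 | 0.30 |
| 0.20 | 0.20 | 0.40 | −0.10 | 0.30 |

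Zero, positive and negative synergy all give the same expected difference.

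**Sample size.** With SD 1 and no loss, the standard error of D is √(2/160) = 0.112. More participants shrink this towards zero and D becomes known exactly, but the rows of the table remain indistinguishable.

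**Other possible sources of information.**
- The tote is at most $100/$10,000 = 1% of the stated value of RtG goods. Like the flyer, it goes to all controls, so it creates no randomised component contrast.
- Process data come from treatment families only, and uptake within that arm is not randomised.

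**Would a factorial have been practical?** Assume a two-sided 5% level, 80% power, SD 1 and no loss, so that the multiplier is 1.960 + 0.842 = 2.802. Four cells of 80 would detect an interaction of 2.802 × √(4/80) = 0.63 SD. The present contrast detects a package effect of 2.802 × √(2/160) = 0.31 SD. An interaction of 0.30 SD would need 4 × (2.802/0.30)² ≈ 349 per cell, or 1,396 in total. The two-arm design is thus the reasonable one at this size, and the wording is what should change.

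**The case against.** The strongest reply is that nothing in the analysis rests on the phrase. Section 1 already gives the purpose as evaluating RtG and measuring its impacts, the research questions ask only about assignment to RtG, and the Lay Abstract asks whether the program makes an impact. No interaction test, component estimate or sample-size calculation invokes synergy. The sum-of-parts wording is also hedged, and the rationale speaks elsewhere of combined value and combined effect, which two arms do estimate.

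Most of this stands, and it limits the severity. It does not remove the error. The hedge in section 1 concerns what the result may be, while the sentence says without reservation that the study will assess the matter. The synergy phrase in the rationale names the quantity outright.

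A reader might infer four stronger things that the documents do not support:

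- *That the trial cannot meet its purpose.* The research questions and the section 1 purpose sentence concern the package effect, which this contrast addresses.
- *That component arms must be added.* The stated questions do not need them, and section 2 describes 160 per group as already enrolled.
- *That the sponsor will present a positive result to funders as synergy.* The Background links funding to RCT evidence of effectiveness, which is a package claim. The synergy statement is addressed to practitioners and policy makers.
- *That dosage data will be used to separate the components.* The process evaluation is for fidelity, dosage and documenting the service for replication. No analysis of dose against outcome is proposed, so no disclaimer about one is needed.

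**Conclusion.** The concern holds as a mismatch between wording and design. The sum-of-parts statements (Background, section 1, Scientific Abstract) and the synergy statement (Rationale: Knowledge Production) describe something this trial cannot estimate. The arm contrast identifies the total effect of the RtG package against no RtG services, with a small tote and a flyer given to controls. It says nothing about whether synergy is positive, zero or negative, whatever the sample size.

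This conclusion rests only on there being two arms and no component-only arm or external component estimate. It does not depend on the 0.30 SD or on the power assumptions, which are illustrative.

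Severity: should fix, wrong as written. It is not a must-fix, because no estimate, test or procedure changes and the research questions remain answerable.

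**What to change.** - In the Background (Study Purpose), Procedures section 1 and the Scientific Abstract, replace the sum-of-parts clause with: *to estimate the effect of assignment to the full RtG package compared with no RtG services (controls receive a gift tote and a mental-health resource flyer)*.
- In Rationale: Knowledge Production, replace the reference to synergistic effects of components with: *the combined effect of the program package*. The same sentence already speaks of testing a combined effect, so this makes it consistent.
- Leave the research questions and the section 1 purpose sentence as they are.
- In reporting, draw no component or synergy conclusions from the two-arm contrast.

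The cost is a text amendment. No data collection, analysis or participant procedure changes. The downside is a narrower headline claim: the trial can say whether the package works, but not that combining its parts is what makes it work.
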